Procedure:

Individual characteristics will be assessed in the initial laboratory session and include a combination of questionnaire and task measures. Daily information, including details on each drinking episode, will be compiled from a combination of EMA morning reports and geospatial data. Finally, within-event variables will be collected from a combination of EMA report and TAC. A key aspect of the project is that the four core AID risk factors from the original project will be assessed under multiple conditions: 1) while participants are sober, 2) during intoxication under controlled laboratory conditions, and 3) while participants are drinking in the natural environment. The method of measurement across different modalities will be as consistent as possible, with appropriate formatting changes when necessary.

Below we describe the assessment of each of these constructs across modalities (see Appendix). AID attitudes (perceived danger of AID). At baseline, participants will indicate how dangerous it is to drive after

consuming 1, 3, and 5 drinks in 2 hours, using a 4-point Likert scale. As in Amlung et al., 2015 & Morris et al., 2014, questions will be linked to estimated BrAC for each participant based on weight and sex.

During the alcohol laboratory session, participants will be asked an in-the-moment version of these questions ("How dangerous it is for you to drive right now?") at multiple points of the BrAC curve.

During the AA portion of the project, participants in the Full AA conditions will be asked to rate the perceived danger of driving "right now" at each of the evening reports after a drink has been reported.

They will also be asked

to provide a retrospective rating of the danger of driving the previous evening during morning reports following a drinking session. Impulsivity. At baseline, participants will complete measures of trait impulsivity (UPPS-P (Cyders et al., 2007), delay discounting (Monetary-Choice Questionnaire; Kirby et

al., 1999) and inhibitory control (cued Go/NoGo; Fillmore et al., 2008). During the laboratory session, they will complete measures of state impulsivity (Momentary Impulsivity Scale (MIS; Tomko et al., 2014)) and delay discounting (5-Trial Adjusting Delay Discounting Task (Koffarnus & Bickel, 2014)) at multiple points on the BrAC curve. They will also complete a measure of inhibitory control (cued Go/NoGo) at matched BrAC's on the ascending and descending limbs. During the AA arm of the project, all participants will complete measures of state impulsivity (MIS) and delay discounting (5-Trial Adjusting Delay Discounting Task) at each evening report. Research Strategy Page 66 Contact PD/PI: [name] Alcohol demand. Behavioral economic demand for alcohol will be assessed at baseline using the

Alcohol Purchase Task (APT; Murphy & MacKillop, 2006). During the laboratory session, demand will be assessed at multiple points of the BrAC curve using three items corresponding to the APT indices (intensity, breakpoint, Omax) developed in Amlung et al., 2015. All participants will also complete these indices in evening AA reports. Subjective intoxication. Participants will rate their level of subjective intoxication, from 1 ("Not intoxicated at all") to 10 ("More intoxicated than I've ever been") (Morris et al.,

2014). During the laboratory session, they will provide this rating at multiple points along the ascending and descending limb of the BrAC curve. During the AA arm of the project, participants will respond at each evening report where drinking is reported and will answer a retrospective version of this question about their previous day's peak intoxication in morning reports. Laboratory Session The laboratory session is estimated to take approximately five hours. Prior to beverage administration, participants will complete a battery of questionnaire measures and computer tasks for baseline assessment. The battery will include a range of measures, including demographics, typical/recent alcohol and substance use and related behaviors, and typical/recent driving behavior. In addition to the measure of the four core constructs (described

above), we will also collect a baseline assessment of Working memory capacity (OSPA; Unsworth et al.,

2005) and AID Perceptions (positive AID expectancies (PEDD-Y; McCarthy et al., 2006), perceived personal limit (Amlung et al., 2016) perceived negative consequences (Grube & Voas, 1996), and normative beliefs about AID (Treloar et al., 2012)). After completing the baseline battery, participants will receive an alcoholic beverage. To minimize participant risk, and consistent with ongoing work in the PI's

lab, we will follow procedures outlined in the NIAAA Recommended Council Guidelines on Ethyl Alcohol Administration in Human Experimentation (NIAAA, 2005). The dose of alcohol will be calculated to produce a peak BrAC of 0.10g% (Curtin & Fairchild, 2003), the equivalent of

approximately 0.85g/kg alcohol for males, 0.73g/kg alcohol for females. This target BrAC was selected to ensure that the majority of participants reach the legal limit of .08g%, given individual variability in metabolism. Further, this dose

level results in an ascending limb period of approximately 60 minutes, which allows sufficient time for the assessment of primary study variables at matched BrAC on the ascending and descending limb (for assessment of acute tolerance) and at peak BrAC. In addition to the four core constructs, during the alcohol session we will also assess BrAC (Alco-sensor FST, Intoximeters, Inc.) at 10 minute intervals on the ascending limb and every 20 minutes on the descending limb to match assessment BrAC for study tasks;

Subjective Response to Alcohol (Subjective Effects of Alcohol Scale; Morean et al., 2013) and AID Intentions (willingness to drive) at multiple points on the BrAC curve. In addition, as part of K25

AA024182 (PI [name]), ongoing work in the PI's lab is focused on developing multiple novel decision making tasks relevant to AID. The laboratory component of the project will include tasks from this line of research that are both associated with AID and sensitive to acute alcohol effects. Ambulatory Assessment The ambulatory assessment arm of the project will involve 6 weeks of data collection for all study participants. During this period, data will be collected via self-report (EMA), the BActrack Skyn (TAC), and location and movement data passively collected from the GPS and accelerometer of the smartphone. Participants will be randomly assigned to two Full AA groups and the MA control group. EMA. During their AA participation, participants will provide self-report data using a study-provided smartphone. Following previous research ([name] et al., 2008a), participants will attend initial orientation sessions to be trained in completing assessments. Participants will return to the lab every 7 days for a brief session to review compliance and receive interim payment, which has proven to increase compliance ([name] et al., 2008b). Participants will complete 5 reports per day – a morning report and 4 “evening” reports. The “evening” reports will be scheduled for 6pm, 8pm, 10pm, and midnight.

However, participants will be able to reschedule or self-initiate the reports if they are consuming alcohol (or using other substances) at other times. The morning report will be scheduled on an individual basis, 30 minutes after participant's self- reported standard waking time. If participants go to bed prior to the midnight assessment, they will

complete a final assessment and put the smartphone to “sleep”, which will terminate follow-up prompts. To

facilitate compliance, assessments are designed to be short, with each assessment requiring less than 3 minutes to complete. For the Full AA conditions, the morning report will include a retrospective report on drinking and transportation the previous day, including drinking location(s), transportation used and options available; social context of drinking episodes (Thrul & Kuntsche, 2015); and intentions/plans for drinking and transportation the Research Strategy Page 67 Contact PD/PI: [name] upcoming evening. For the evening reports, participants will report on their mood, craving, core study variables, current drinking behavior (if any) and AID intentions. When participants do not report drinking, additional “filler” questions on current mood will be assessed to equalize time to complete the report. For

the MA control condition, participants will complete abbreviated versions of each report, with no questions

specific to AID. The morning report will ask about drinking location, transportation, and social context the previous day, with no questions on plans/intentions. The evening reports will assess mood, craving, core study variables (except for AID attitudes), and current drinking behavior. In addition to the four core constructs, the EMA Evening Assessments will also include: Mood. Questions from the Positive and Negative Affect Schedule (PANAS-X; Watson & Clark, 1999); Alcohol craving. Using a single 100-point visual analog scale, asking “How much do you want a drink right now?”; Social Context. Participants will be provided a list of who they are currently with and asked to check all that apply, including 1) romantic partner, friend, coworker, child(ren), parent, other family, someone else. This measure is used in EMA studies of drinking behavior by Co-investigator [name] (Lane et al., 2015); AID Intentions. Will be assessed at each evening assessment for those in the Full AA conditions.

Transdermal Alcohol Concentration (TAC). TAC measurement will be taken continuously by the Skyn. All participants will be asked to wear

their Skyn throughout the AA assessment period, but particularly during drinking episodes. A change in the revised application is that participants will not be able to see their current TAC at any time. However, for participants in the Full AA conditions, once the Skyn registers that they have reached .05 g/dl TAC, the app will prompt them to consider alternative transportation. Clickable links for local taxi/ride services will also be presented. Participants will be told that this prompt is based on their current TAC, and that it indicates it is not safe for them to drive, but will not be told the TAC trigger for this prompt. As noted, participants will wear the Skyn during their laboratory alcohol session. This will allow us to collect data on the accuracy of the Skyn's TAC estimates and, if necessary, develop individualized algorithms for estimating BrAC from TAC. Geospatial data. Throughout the AA assessment, participant location and movement data will be passively recorded on the study-provided smartphone. At the end of the AA period, this data will be combined with EMA data. When a participant reports drinking (or records a positive TAC), information about their drinking location, distance from home, travel using a motor vehicle, and what time they

returned home will be recorded. The most recent evidence for the accuracy of cellphone GPS systems indicate sufficient precision for our proposed use (Zandbergen & Barbeau, 2011). Using a much earlier generation of smartphones, they concluded that position estimation errors were uncommon, for example finding that horizontal location errors ranged from 5-21 meters in the least ideal conditions (static indoor testing). Data were more precise when moving outdoors, due to the clearer access to satellite data. Based on

this, we will use this geospatial information to provide a validity check on participant self-report. Discrepancies between participant selfreported location, use of motor vehicle, etc., will be probed during their next TLFB interview. As noted, [name] will provide the project with a database of GPS locations for all nearby licensed drinking establishments

Statistical Analyses and Power:

Aim 1. Integrating laboratory and event-level predictors of AID. For Aim 1, we will employ a two-part (hurdle) model to test laboratory and AA predictors of AID. Part one of the model examines predictors of engagement in AID (or driving after any drinking). For this part of the model, we will employ a mixed logistic model examining factors that are predictive of a dichotomous variable indicative of whether, for a given drinking event, a participant drives after drinking alcohol. The second part of the model will employ a Gaussian linear mixed model, and examines predictors of a participant's TAC/BrAC level at the time of driving for drinking events where driving is reported. This analytic approach provides us with both increased flexibility and precision in our analyses. For example, we will be able to identify predictors of driving after any drinking as well as predictors that may be specific to driving at higher TAC. We believe that this flexibility is an important improvement to our approach in the revised application. For example, Hypothesis 1.3 will examine whether contextual factors increase the influence of AID risk factors on the likelihood of AID. Hypothesized contextual factors are based on studies demonstrating that drinking location (fewer miles to home; Kelley-Baker et al., 2013) and venue (drinking in restaurants; Gruenwald et al., 2002) are associated with increased AID risk. Our two-part model will allow us to test whether, for example, drinking venue increases the effect of AID risk factors for driving after any drinking, while drinking location increases the effect of AID risk factors when predicting driving at higher TAC/BrAC. In addition to examining TAC/BrAC at time of drinking as a continuous attribute, our approach will allow us to examine rational cutpoints for TAC – specifically, we will test models for cutpoints of TAC/BrAC of the current U.S. legal limit (.08) and NHTSA's proposed limit (.05). Research Strategy Page 68 Contact PD/PI: [name] Both models will have two levels, comprised of drinking events within participants. We will estimate models via both Maximum Likelihood methods and Generalized Estimating Equations; the former method can result in more accurate parameter estimates in certain situations (Stroup, 2013), whereas the latter method can be more flexibly extended to assumption violations (e.g., variance heterogeneity). Modeling will proceed by first fitting baseline GLMMs that establish associations between lower-level measures and the DV. The lower-level measures will be at the event level (including such variables as drinking venue), so they will directly address Hypothesis 1.2. Once these lower-level associations are established, we will then incorporate laboratory measures to address Hypothesis 1.1, followed by interactions to address Hypothesis 1.3. For example, consider studying the relationship between event-level impulsivity and AID. We will first person-center the impulsivity variable, so that the associated regression weight provides information about the effect of impulsivity as a participant departs from his/her mean level of impulsivity. We will then establish an association between impulsivity and AID using a two-level logistic model, where multiple eventlevel variables are included as IVs. The models will account for individual differences in associations between the event-level variables and AID, and they will be further extended (using level-2 IVs and cross-level interactions) to study the laboratory-based effects and moderation effects from Hypotheses 1.1 and 1.3. We will fit multiple versions of the models using different subsets of IVs, in order to establish that effects are robust to choice of predictors. This is important because unmodeled heterogeneity (resulting from omitted predictor variables) can adversely impact model estimates (Mood, 2009). To estimate power associated with these models, we adopted a simulation-based approach (Gelman & Hill, 2007). This involved generating artificial data from an assumed true model, fitting the proposed GLMM to each artificial dataset, and computing power based on the results. To estimate our power to detect an association between event-level impulsivity and AID, we specified parameter values for the true model based on previous studies. First, based on pilot data, we assumed that participants report driving following 15% of drinking events. We also assumed that each 5- point increase in impulsivity (as measured by delay discounting) was associated with (i) a 10% increase in the odds of driving after drinking (the low end of observed effect sizes for core study constructs) and (ii) a BrAC increase of .01, with random participant effects included in “maximal” models (Barr et al., 2013). In using these parameter values along with the anticipated sample sizes, our estimated power to detect these

associations is .91 in the logistic model and .99 in the linear mixed model. If Aim 2 is realized, then we can only use half of the Full AA group (the half that does not receive AA for the first six weeks), along with the

MA control group, to assess raw associations between lower-level variables and AID. In this case, we estimate power of .85 and of .99 to detect the associations (using the same values as above with a reduced sample size). We computed additional power estimates for moderation Hypotheses 1.3, using both the logistic model (where AID is a binary DV) and the Gaussian model (where TAC/BrAC is the DV). We assumed that Aim 2 was not realized, reducing the overall number of participants that we could enter into the analysis. For the logistic model, we assumed (as above, based on pilot data) that each 5-point increase in impulsivity was associated with a 10% increase in the odds of driving after drinking. We further assumed that this relationship was moderated by drinking venue, such that the relationship was diminished when participants were drinking at a restaurant. Under this scenario, power was .77 for the moderation

effect. For the Gaussian model, we assumed (as we did above) that each 5-point increase in impulsivity was associated with a mean BrAC increase of .01. We further assumed that this relationship was moderated by drinking location, such that the relationship was absent if a person was drinking 10 or more miles from home. Under this scenario, power was .96 for the moderation effect. Aim 2. Test potential effects of AA on AID behavior and intentions. For Aim 2, the study design affords us multiple manners in which we can examine the potential of mobile technology as an intervention for AID. We can estimate the effect of AA prospectively, examining whether or not AID changes from before a participant receives AA to after. We can also estimate the effect across experimental groups, examining whether or not AID differs between the groups with Full AA and the MA control group. To address this question, we will again employ the two DVs of driving after drinking and TAC in separate GLMMs (where drinking events are nested within participants). The IVs in each model will be dummy variables that are related to each participant's condition and to the time within the study. Specifically, the dummy variables will reflect whether or not the

individual is currently receiving AA, as well as whether or not the individual ever previously received AA. This will allow us to disentangle the effect of currently receiving AA from effects that may last after the individual has received AA. In computing power, we assumed 100 participants receiving AA at differing times (as described in Overview of Proposed Work) coupled with 100 participants in the control group. We further assumed that (i) active reception of AA reduces driving after Research Strategy Page 69 Contact PD/PI: [name] drinking from an average of twice per month to an average of 1.5 times per month (with individual differences in this effect), and (ii) active reception of AA reduces TAC of driving events by an average of .01. In employing assumption (i) in a logistic mixed model, we obtained a simulation-based power estimate of .79 to detect an intervention effect of active AA. In employing assumption (ii) in a Gaussian linear mixed model, we obtained a simulation-based power estimate of .97 to detect the intervention effect.

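### The Aim 2 models leave out baseline drinking and driving measures that the trial already collects, giving up a modest amount of precision at no saving

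*Combined protocol and SAP*

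**What the plan says.** Procedure (opening paragraph and Laboratory Session): "Individual characteristics will be assessed in the initial laboratory session". The battery completed before the beverage covers a range of measures, "including demographics, typical/recent alcohol and substance use and related behaviors, and typical/recent driving behavior". These data therefore predate the ambulatory period and cannot be affected by it.

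Procedure, Ambulatory Assessment: "Participants will be randomly assigned to two Full AA groups and the MA control group". No allocation method is given, and no stratification factor is named or ruled out.

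Statistical Analyses and Power, Aim 2: driving after drinking and TAC are analysed in separate GLMMs, "where drinking events are nested within participants". On predictors: "The IVs in each model will be dummy variables that are related to each participant's condition and to the time within the study". The text then specifies two dummies, for current and for previous receipt of AA. No baseline covariate is mentioned. Two comparisons are planned: Full AA against MA control, and a prospective one, "examining whether or not AID changes from before a participant receives AA to after".

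Statistical Analyses and Power, Aim 1: the same kind of two-level model is extended with laboratory measures as level-2 predictors, and the text warns that omitting predictors can harm the estimates. Aim 2 has no matching provision, and no reason is given for the difference.

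**The concern.** How often a person drinks and drives before the study should predict how often that person drives after drinking during it. A random intercept allows for such differences between people but does not explain them, so they stay in the standard error of any comparison between people. The Full AA against MA comparison is of that kind, because MA participants have no AA period of their own to compare with.

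At stake is the lower of the two Aim 2 power figures, .79 for driving after drinking. The trial already holds data that could raise it without more participants or assessments.

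**Working it through.** **Inputs from the documents.** Driving follows 15% of drinking events (Aim 1 power text). AA lowers driving after drinking from 2 to 1.5 times a month, with 100 AA and 100 control participants and stated power .79 (Aim 2 power text). The observation period is six weeks (Ambulatory Assessment). One half of the Full AA group has no AA in the first six weeks (Aim 1 power text).

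**Inputs not given, so assumed.** Two-sided alpha .05; SD of the AA effect between people, σ, from 0 to .5 on the log-odds scale; share of person variance explained by baseline, R², of .10, .25 or .50. The between-person SD, τ, is also not given and is solved for below.

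**Planned effect.** Drinking events per month = 2/.15 = 13.3. The rate under AA = 1.5/13.3 = 11.25%. Odds ratio = (.1125/.8875)/(.15/.85) = .718, log −.331. Events in six weeks: 13.3 × 42/30.4 ≈ 18.4 per person.

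**Sampling variance of one person's log-odds.** Without AA: 1/(18.4 × .15 × .85) = .426. With AA: 1/(18.4 × .1125 × .8875) = .544.

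**The plan's .79.** Treating events as independent gives .82 for one month of events and .92 for six weeks. With person variation, a parallel 100 v 100 comparison has

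Var = [(τ² + .426) + (τ² + σ² + .544)]/100, and power ≈ Φ(.331/SE − 1.96).

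Power of .79 needs SE = .1196, so Var = .01430. With σ = 0, 2τ² = 1.430 − .971 = .460 and τ = .48. The figure is plausible but cannot be confirmed, because τ is unstated.

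**Adding the covariate.** Replace τ² by τ²(1 − R²). With σ = 0 and R² = .50, Var = (.230 + .971)/100 = .01201, SE = .1096, .331/.1096 = 3.02, and power is .855.

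The same was done for a staggered layout: 50 with AA then none, 50 with none then AA, and 100 MA followed in both periods. It used generalised least squares on person-period log-odds, with period, current-AA and previous-AA terms. In every row τ is set so that unadjusted power is .79.

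| Layout | σ | τ needed | R² .10 | R² .25 | R² .50 |
|---|---|---|---|---|---|
| Parallel | 0 | .48 | .803 | .822 | .855 |
| Parallel | .25 | .45 | .801 | .818 | .846 |
| Parallel | .50 | .32 | .796 | .805 | .820 |
| Staggered | 0 | .92 | .803 | .825 | .868 |
| Staggered | .25 | .85 | .803 | .823 | .864 |
| Staggered | .50 | .67 | .800 | .816 | .846 |

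The variance of the AA effect falls by 2 to 3% at R² .10, 4 to 9% at .25 and 7 to 19% at .50.

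**Checks.** A simulation of the parallel layout (1,500 replicates, 18 events each, τ = .5, σ = .25) moved power from .70 to .73 at R² .25 and from .71 to .78 at R² .50. Its level is lower than the formula's, but the gain is of similar size. If MA participants are followed for only one six-week period, .79 is reached only with τ near .15 and σ = 0. The gain is then under one point (.792 to .798).

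**The case against.** The strongest reply is that the model already deals with differences between people. Events are nested within participants, and the power figure comes from simulating a mixed model, so chance differences between groups are already in its standard error. Part of the AA estimate is also within-person, from the before/after comparison in the Full AA groups, and baseline history adds little there. R² is an assumption with no support in the documents. All of this stands, and it keeps the gain small. It does not remove it: the staggered layout above includes the within-person part and still gains.

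Three stronger readings are tempting but not supported.

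- A reader might infer that chance imbalance distorts the AA effect. Under random assignment it does not bias the test; it is ordinary sampling error, already counted.
- A reader might infer that allocation is unstratified and should be stratified on drink-driving history. The text says only that assignment is random and refers for the design to an Overview of Proposed Work that is not in the supplied documents. The battery also names drinking and driving but no drink-driving frequency.
- A reader might pair a large person SD with the .79 starting point and compute a much larger gain. The two do not fit together in a purely between-group comparison. Using .43 as the within-person variance in both arms, unadjusted 100 v 100 power is .81, .50 and .30 at τ = .5, 1 and 1.5, so only a τ near .5 fits .79.

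**Conclusion.** The omission is real and worth correcting, but it is a modest loss of efficiency and not a flaw in validity. For driving after drinking, adjustment would move power from .79 to about .80 at R² .10, .81 to .83 at R² .25, and .82 to .87 at R² .50. These figures rest on the assumed alpha, σ and R², on τ being calibrated to the plan's own .79, and on either a parallel comparison or MA follow-up in both periods.

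If person variation is larger than .79 implies, the plan starts from lower power and gains more. At τ = 1.0 and σ = .25, staggered power goes from .75 to .79 (R² .25) or .83 (R² .50).

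No gain was calculated for the TAC model. At a stated power of .97 there is little room for one.

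That baseline measures are collected and that no Aim 2 covariate is named can be read directly from the text. The size of the gain is conditional on the assumptions.

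**What to change.** In the Aim 2 analysis text, pre-specify baseline drinking frequency and baseline driving frequency as level-2 covariates in both GLMMs, in the way Aim 1 already brings in laboratory measures. Name the battery items and their coding. Add prior drink-driving frequency if the battery contains it. Fix the choice before outcome data are examined by group, and keep the dummies-only model as a sensitivity analysis.

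The power text should also state the between-person SD, the SD of the AA effect and the alpha used in the simulation, so that the gain can be recalculated.

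The cost is a few sentences and two or three model terms. It needs no new data, participants or visits, and it works even if assignment is complete.

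### A reported drive made without the Skyn has no TAC value, and avoiding the Skyn-triggered prompt could make such gaps commoner in Full AA, so the Aim 2 TAC comparison needs a wear record and a planned missing-TAC analysis

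*Combined protocol and SAP*

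**What the plan says.** All references are to the combined protocol and SAP.

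- **Source of TAC** (Procedure, Transdermal Alcohol Concentration): "TAC measurement will be taken continuously by the Skyn". No other field source is described. The individual calibration mentioned there converts TAC to BrAC, so it also needs the device.
- **Wear** (same section): all participants are asked to wear "their Skyn throughout the AA assessment period, but particularly during drinking episodes". No minimum wear and no definition of non-wear is given.
- **Prompt** (same section): "for participants in the Full AA conditions, once the Skyn registers that they have reached .05 g/dl TAC, the app will prompt them" to consider other transport. "Participants will be told that this prompt is based on their current TAC" and that it means driving is unsafe. They cannot see their TAC and are not told the trigger value. The MA control group has no prompt.
- **Outcome** (Statistical Analyses and Power): the second part of the Aim 1 model "examines predictors of a participant's TAC/BrAC level at the time of driving for drinking events where driving is reported". For Aim 2, "we will again employ the two DVs of driving after drinking and TAC in separate GLMMs".
- **Drink reports** (Procedure, EMA): both arms report current drinking. For MA control, "The evening reports will assess mood, craving, core study variables (except for AID attitudes), and current drinking behavior". Weight and sex are available, since for the baseline attitude items "questions will be linked to estimated BrAC for each participant based on weight and sex".
- **Compliance** (Procedure, EMA): a laboratory visit every 7 days reviews compliance and pays participants. No Skyn criterion is stated.

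The text does not say how a drive without a TAC reading is handled, whether non-wear is told apart from zero TAC, or whether wear is compared between arms.

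**The concern.** One device delivers part of the intervention and measures an outcome of that intervention. In MA control, taking it off loses only a measurement. In Full AA it also silences the prompt, which gives those participants an added reason to leave it off, most of all on heavier nights. The missing value would then depend on the unseen TAC, and more so in one arm.

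The planned estimators do not repair this. Maximum likelihood requires that missingness not depend on the unseen TAC given the observed data, and unweighted GEE requires more than that. The before/after comparison in Aim 2 is exposed as well, because the prompt belongs to the Full AA condition. The bias would run in the direction of the hoped-for result, a lower TAC of driving events. Without a wear record, the trial could not later separate the two explanations.

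This differs from AA preventing a drive. Here the drive took place and was reported, but its TAC is unknown.

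**Working it through.** **1. The plan's own figure.** Aim 2 states power of .97 for a .01 reduction in TAC of driving events, with 100 participants receiving AA and 100 controls. Alpha, the TAC SD, the variance components and the number of events are not given, so the figure can be neither reproduced nor refuted. Assuming two-sided alpha of .05, it implies

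SE = .01 / (1.960 + 1.881) = .0026,

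that is, an SD of participant means of .0026 / √(2/100) ≈ .018. That is possible. This SE is used below as the plan's implied precision.

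**2. Shift from selective non-wear, with no true effect.** Let M be the mean TAC of all drives, p the share at or above .05, H the mean of that share, and q the extra fraction of that share lost in Full AA only. Then

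shift = −q·p·(H − M) / (1 − q·p).

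The documents give no TAC distribution and no wear rates, so these are assumptions: normal, truncated at zero, location .05.

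- SD .03: p = .525, M = .0531, H = .0739. For q = .30: .30 × .525 × .0208 / (1 − .1575) = .0039.
- SD .02: p = .503, M = .0504, H = .0660. For q = .10: .10 × .503 × .0156 / (1 − .0503) = .0008.

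| Extra loss q | Fall in mean, SD .02 | Fall in mean, SD .03 | Share of the planned .01 |
|---|---|---|---|
| 10% | .0008 | .0012 | 8–12% |
| 20% | .0017 | .0024 | 17–24% |
| 30% | .0028 | .0039 | 28–39% |
| 40% | .0039 | .0055 | 39–55% |

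With locations of .04 to .06 and SDs of .02 to .04, the 30% row runs from .0023 to .0048.

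**3. Chance of a false significant difference.** This is Φ(b/SE − 1.96) + Φ(−b/SE − 1.96) for a shift of size b and SE = .0026. A shift of .0012 gives about 7%, .0024 about 15% and .0039 about 32%, against a nominal 5%. The SE is held fixed, so these are approximate.

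**4. Removal that follows TAC only roughly.** Step 2 deletes only values at or above .05, which is the sharpest form of selection. Suppose instead that the same share of drives is lost according to a perceived intoxication that correlates .5 or .7 with TAC. The 30% case with SD .03 then falls from .0039 to about .0019 or .0027.

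**5. When there is no bias.** If non-wear is unrelated to TAC, or depends on TAC equally in both arms, the shift under no effect is 0. Only power is lost. With 30% of drives missing, .97 becomes about .90 to .95.

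**6. What drink-based imputation recovers.** In the 30% case with SD .03, regression imputation from a proxy that correlates .5, .7 or .85 with TAC leaves a bias of .0029, .0020 or .0011, compared with .0039 for complete cases.

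**The case against.** The strongest reply is that differential removal is inferred, not observed. Participants cannot see their TAC and do not know the trigger, so they cannot time removal to .05. They would have to anticipate the prompt, or learn from an earlier one. The prompt can also simply be ignored. MA participants, who get nothing from the device in the field, might wear it less, so even the direction is not certain. This stands. It is why the size is given as a range under assumptions and why step 4 matters. It does not remove the concern, because Full AA participants know that the device drives the prompt and have six weeks in which to learn when it appears.

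The weekly visits are a partial safeguard in both arms, but no Skyn criterion or analysis consequence is attached to them. The TLFB interview is used to probe discrepancies in matters such as location and vehicle use; nothing says that it replaces TAC.

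Two further limits also stand. Dropping a drive without TAC is the model's default, not a rule the plan states. Scoring non-wear as zero would be another possibility, and under the same differential removal it would bias in the same direction. Also, the text refers to an overview section and an appendix that it does not contain, so a wear rule may exist there.

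A reader might infer that Full AA participants will remove the device more often, or that any TAC reduction in this trial would be an artefact. The documents contain no wear data and support neither statement.

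**Conclusion.** The point holds as a structural weakness of the TAC outcome. Reported drives without the Skyn have no TAC, the prompt gives Full AA an added reason for such gaps, and the text has no means of detecting or handling them. If an extra 10% to 40% of Full AA drives at or above .05 are lost, the spurious reduction is about .001 to .0055 with an assumed location of .05 and SD of .02 to .03. It is less if removal is only loosely related to TAC, and zero if removal is unrelated to TAC or alike in both arms.

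It would go too far to conclude that Aim 2 as a whole is compromised or that the power of .97 is wrong. Driving after drinking does not need a TAC reading where drinking is self-reported, so that outcome is largely unaffected. The .97 is not contradicted by anything in the documents. What is affected is the Aim 2 TAC model and, through missing values, the Gaussian part and the TAC cutpoints of Aim 1. The change is worth making because wear that was not recorded cannot be reconstructed afterwards.

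**What to change.** 1. Add a 'Skyn on now?' item to every EMA report in both arms, or use a device wear record if one is available.
2. Code non-wear as missing, never as zero TAC.
3. Tabulate wear on drinking nights, and on reported drives, by arm and AA period.
4. Prespecify a sensitivity analysis for the Aim 2 TAC model and the Gaussian part of Aim 1 that keeps every reported drive. Multiply impute missing TAC from a BrAC estimated from evening-report drinks, sex, weight and GPS drive time, calibrated on drives that have both values. Use evening reports only, so that the source is the same in both arms.
5. Add a tipping-point analysis that shifts the imputed TAC of Full AA drives upwards until the conclusion changes. Imputation alone assumes that missingness is explained by the reported drinks, and someone avoiding the prompt may also under-report drinks.
6. First confirm that evening reports capture the number and timing of drinks in both arms. The text says only that current drinking behaviour is assessed.

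Whether imputed or complete-case TAC should be primary is a matter of preference; what matters is that both are specified in advance.

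The cost is one EMA item, modest programming and some plan wording, with no extra visits or participants. Imputed values carry self-report error, so standard errors rise slightly. The bias is reduced and made visible, not removed.
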